## **7.4 Analyses**

### **7.4.1 Demographics and Baseline Characteristics**

Demographics and baseline characteristics will be summarized via descriptive statistics.

### **7.4.2 Safety Analyses**

To assess safety, we will summarize the incidence of adverse events for the study group. Analysis of safety is included as a secondary endpoint. All subjects who receive a dose of abatacept will be evaluated for safety. Safety outcomes include adverse events, clinically significant changes in vital signs, laboratory test abnormalities, and clinical tolerability of the drug. The investigator will determine the severity of each adverse event as mild, moderate, severe, or very severe. Laboratory findings that the investigator feels are clinically relevant should be recorded as adverse events. In addition, the investigator will determine the relationship of the adverse event to the administration of the study drug. Any occurrence of a SAE from time of consent forward, up to and including follow-up visits will be reported. See Section 6.5 for the SAE reporting procedures.

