|   | 
lack of existing evidence-based data for any treatment in alopecia areata, there is a strong rationale for testing CTLA4-Ig treatment in this disease.
  |
| 
Study Objectives:
 Primary:
 Secondary:
             | 
The study's primary efficacy endpoint will be the proportion of responders after 6 months of treatment, with response defined as 50% or greater hair re-growth from baseline as assessed by SALT score at week 24. This is a relatively strict definition for defining responders and non-responders and was chosen to minimize the potential for spontaneous remission, in which fewer than 10% are expected to achieve this magnitude of hair regrowth spontaneously.
 
As secondary endpoints, efficacy will be measured by changes in hair re-growth as a continuous variable as determined by physical exam and Canfield photography, as well as patient and physician global evaluation scores. To assess the durability of responses, patients will continue to be followed for an additional 6 months off treatment or until it is determined that relapse has occurred. Additionally, patient reported outcomes, safety measures, incidence and timing of relapse will be important secondary outcomes. We will also explore the efficacy of treating 2 patients with current alopecia totalis or universalis, and in doing so, will compare, on an exploratory basis, the rate of occurrence of hair regrowth in patients with moderate to severe patch type alopecia areata compared to those with current alopecia totalis or universalis.
 
In addition, response to abatacept treatment will be examined on an exploratory basis for correlation with the presence or absence of the AA GWAS risk haplotype.
 |
| 
Study Design:
   | 
Open label pilot study of 6 months of abatacept 125mg SC per week in the treatment of moderate to severe AA and current alopecia totalis or universalis, followed by 6 months follow-up off drug to assess the incidence and timing of recurrence of disease. Treatment may be extended by up to 6 additional months beyond the initially planned 6 months of treatment if clinically indicated at the discretion of the investigator.
  |

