| 
Study Schema
 Drugs / Doses /
 Length of Treatment)
 | 
A fixed dose of abatacept (125mg) will be self-administered subcutaneously weekly for 24 weeks, with an option to extend treatment for up to an additional 24 weeks at the discretion of the investigator. A loading IV dose will not be employed.
  |

|  |  |
|--|--|
| Accrual Goal:
(Total number of subjects)              | 15   |
| Accrual Rate:
(Number of subjects expected per month) | 1-3  |
| FPFV:
LPFV:
Follow Up:
(dd-mm-yy)             | May, 1, 2013
March 31, 2015
12 months  |
| Correlative Studies:
(PK/PD, etc.)                    | 
Our published work and previous studies in human AA have reported increased NKG2DL expression and augmented expression of IFN response genes in the target hair follicle end organ, and elevated NKG2D expression in circulating CD8 T cells and NK cells (Ito et al, 2008; Petukhova et al, 2010).
 
Clinical Correlative Studies
 
Our study will include longitudinal assessment of AA biomarkers at baseline and during treatment to correlate treatment and disease status with;
 
 
1) histological improvement with reduced T cell peribulbar infiltrates.
 
2) declines in circulating and peribulbar CD8+NKG2D+ infiltration and in follicular hair follicle NKG2DL expression.
 
3) reduced IFN inflammatory biomarkers in the skin and blood.
 
4) presence or absence of AA GWAS risk haplotype
 
 |

|                                   |  |
|-----------------------------------|--|

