### **Week 25 to 48 (follow-up period off study medication)**

All patients will be seen at week 36 and 48, after completion of 6 months of study drug, to determine durability of response or evidence for a delayed effect. Importantly patients who achieved  $\geq$  50% regrowth as measured by SALT score (responders) will be seen at week 36,

and 48 after end of study treatment in order to assess the frequency and timing of relapse or to capture the occurrence of further regrowth.

Relapse will be defined as any recurrence of hair loss in responders (subjects achieving greater than 50% decrease in SALT score from baseline during the first 6 months of the study) who had achieved stable regrowth without continued loss for at least 2 months; and loss of  $\geq$  25% of regrowth in patients who had achieved 50% regrowth during treatment but still had chronic low grade hair loss.

Nonresponders will also continue follow-up in order to assess for delayed response.

Efficacy evaluations: SALT, PGA, Patient global assessment and patient quality of life assessment will be performed at Weeks 36, and 48.

Blood draws for safety parameters will be conducted at week 30 if deemed necessary to assess normalization of any previously abnormal values.

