### Weeks 40 to 72 (Observational Period after Extension Option)

Visit days will have an acceptable window of  $\pm 7$  days.

- Patient will be observed at 12 and 24 weeks after completing study medication
- Vital signs, body weight
- Physical and dermatological examination (at end of study)
- Adverse events reporting, concomitant medication review
- Photography
- Physician evaluation utilizing the PGA and SALT scale
- Patient global assessment and quality of life assessment
- Optional Scalp biopsy (4mm punch biopsy) – at the discretion of the principal investigator and with the consent of the subject, based upon perceived utility in context of individual patient response to therapy and durability of that response.
- Optional Blood collection for immunological studies, at the discretion of the principal investigator and with the consent of the subject.

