#### Secondary efficacy outcomes in detail

1. Percent hair regrowth from baseline determined by SALT measurements following 12, 24 weeks of treatment and during the observational phase at weeks 36 and 48.
2. Comparison of the proportion of responders in the experimental group with the historically known placebo response rate ( $<10\%$ ), with response defined as 50% change in SALT score (50% regrowth) from baseline, at weeks 12, 36 and 48.
3. Comparison of the proportion of subjects in the experimental group and the proportion of subjects in the historical control group attaining global overall improvement SALT score of A5 (100% coverage) supported by  $\leq$  SALT 25 at weeks 12, 24, 36 and 48.
4. Change in PGA (Physician Global Assessment) based on evaluation of live evaluations and standardized photographs between baseline, week 12, 24, 36 and 48.
5. Change in patient global assessment between baseline, Week 12, 24, 36 and 48.
6. Change in patient quality of life assessment from baseline to weeks 12, 24, 36 and 48.
7. Frequency of occurrence and timing of relapse (as defined above) in responders followed for 6 months off therapy.
8. Safety will be evaluated as a secondary endpoint using descriptive statistics to summarize the cumulative incidence and types of AEs.
9. The proportion of patients who discontinued treatment will be summarized.

[figure not shown]

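### Adverse events are summarised as one incidence for the group although on-drug and follow-up time differ between subjects, so the figure depends on the number extended as well as on the drug

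*Combined protocol and SAP*

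**What the plan says.** **The summary.** Section 7.4.2 states: "To assess safety, we will summarize the incidence of adverse events for the study group". Section 7.3 item 9 repeats this. Section 6.4.2 item 8 is more specific: "Safety will be evaluated as a secondary endpoint using descriptive statistics to summarize the cumulative incidence and types of AEs". The safety population is everyone dosed: "All subjects who receive a dose of abatacept will be evaluated for safety". No section defines a treatment-emergent window, separates on-drug from off-drug events, fixes a common observation period or uses person-time.

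**Time on drug.** The synopsis sets weekly dosing "for 24 weeks, with an option to extend treatment for up to an additional 24 weeks at the discretion of the investigator".

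**Time off drug.** For subjects not extended, Section 4.1 (Week 25 to 48) says "All patients will be seen at week 36 and 48, after completion of 6 months of study drug". For extended subjects, Section 6.1 says "Patient will be observed at 12 and 24 weeks after completing study medication". Section 4.1 provides for AE assessment at every visit and for monthly telephone contact about AEs in the observational phase.

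**Where the extension was carried through.** The secondary outcome list in Section 2.2 mentions the extension. The lists in Sections 6.4.2 and 7.3 do not, and Section 7 does not mention it at all. Section 7.3 item 2 still treats weeks 36 and 48 as after the end of treatment, although an extended subject may be on drug then.

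**The concern.** A cumulative incidence has a meaning only together with the time over which subjects were observed. Here that time differs between subjects in two ways.

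- On-drug time runs from 24 to 48 weeks for completers and is shorter for early stoppers. Who gets more is a discretionary choice, so extension-period events come from a selected subset.
- Off-drug time enters the same figure by default, since no window excludes it, and its length is not settled. Section 4.1 has all patients, nonresponders included, continue follow-up; Section 6.4.2 does not require nonresponders to take part. Section 6.7.1 ends routine SAE collection 30 days after the last dose; Section 7.4.2 reports SAEs through the follow-up visits. Section 6.7.3 gives a start for nonserious AE collection but no end.

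Safety is a named secondary endpoint, and descriptive figures are the main product of this pilot. A single proportion that changes with the number extended is hard to interpret and hard to carry into the design of a later trial.

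**Working it through.** The plan gives no AE incidence or safety precision figure, so there is none to reproduce. Its one design figure, the power for the response rate, has no bearing here.

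**Inputs.** N = 15 (Section 7.1). On-drug time is 24 weeks, or 48 if extended in full (synopsis). Off-drug time is taken as 24 weeks for everyone, although the documents conflict on this. The illustrative event rate is the 32% of subjects with infections over the 4-month period of the subcutaneous RA study IM101173 (Section 1.3.4). The half-life is 11.2 to 14.7 days (Section 1.3.2). Assumptions: constant hazard and no dropout.

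**Step 1, weekly hazard.** 4 months = 4 × 52/12 = 17.3 weeks. L = −ln(1 − 0.32)/17.3 = 0.0222 per week.

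**Step 2, incidence over t weeks.** 1 − exp(−L·t) gives 41.4% at 24 weeks, 65.6% at 48 and 79.9% at 72.

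**Step 3, group figure with k of 15 extended.** On drug only: [(15 − k) × 41.4% + k × 65.6%]/15. With off-drug weeks at the full rate: [(15 − k) × 65.6% + k × 79.9%]/15. At half the rate, 24 off-drug weeks count as 12.

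| k extended | On-drug subject-weeks | Total subject-weeks | On drug only | Off-drug pooled, half rate | Off-drug pooled, full rate |
|---|---|---|---|---|---|
| 0 | 360 | 720 | 41.4% | 55.1% | 65.6% |
| 5 | 480 | 840 | 49.5% | 61.3% | 70.4% |
| 10 | 600 | 960 | 57.5% | 67.5% | 75.1% |
| 15 | 720 | 1080 | 65.6% | 73.7% | 79.9% |

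The shift from none to all extended is 24 points on drug only, 19 points with off-drug weeks at half rate and 14 at full rate. With 5 extended, the shifts are 8, 6 and 5 points.

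**Step 4, other event rates.** For assumed 24-week on-drug risks of 10%, 20%, 40%, 50% and 60%, extending everyone gives 19%, 36%, 64%, 75% and 84%. The shift is 9 to 25 points.

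**Step 5, summaries that stay put.** Under the same model, the weeks 0-24 incidence is 41.4% for every k, and the on-drug rate is 2.2 first events per 100 subject-weeks at risk for every k.

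**Step 6, time after the last dose.** Section 6.10.2 uses six half-lives as the exposure interval for pregnancy. Borrowed here only for scale, that is 6 × 11.2/7 = 9.6 to 6 × 14.7/7 = 12.6 weeks. A 24-week off-drug period is therefore partly exposed and partly not, and the plan does not say how events in it are to be classed.

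**The case against.** The best case against this point is that the study is a 15-subject descriptive pilot with no safety hypothesis, no comparator and no AE-based decision rule. Only Section 6.4.2 uses the word cumulative, and nothing forbids tables by period. Severity and relationship to drug are recorded as well. A moderate number of extensions also moves the figure by less than its sampling noise: at 41.4% with n = 15 the standard error is √(0.414 × 0.586/15), about 13 points, against 5 to 8 points with 5 extended.

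Most of this stands as a limit on severity. It does not remove the point. Severity and relatedness do not adjust for time at risk, and leaving the periods to be chosen after the data are seen is easily avoided.

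A reader might infer more than the documents support:

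- *That extension goes to subjects who are doing well.* The text says only that it may be given if clinically indicated, at the investigator's discretion, which fits slow or partial responders equally well. Only non-random selection is supported.
- *That the figure follows the number extended and not the drug.* Under the model above it depends on both.
- *That the shift is about 24 points.* That is on-drug time only, comparing nobody with everybody extended. Pooling off-drug weeks reduces it to 14 to 19 points.
- *That a planned comparison with the 4-month RA study is spoiled.* No such comparison is planned, and a weeks 0-24 table would not match its window either.

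**Conclusion.** The point holds, at moderate weight. The stated AE summary pools unequal on-drug time with off-drug time of unsettled length, so the same underlying rate gives different figures according to how many subjects are extended. In the illustration, on-drug incidence is 41% with none extended, about 50% with 5 of 15 and 66% with all. Pooled with off-drug weeks at the full rate, it runs from 66% to 80%. These figures rest on a constant hazard, no dropout, 24 off-drug weeks for everyone and an infection rate from an RA population. They show sensitivity and do not predict this trial's results. The harm is to the interpretation of a descriptive secondary endpoint; the efficacy analysis and error control are untouched.

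**What to change.** In Sections 7.4.2, 7.3 item 9 and 6.4.2 item 8, replace the single group incidence with separate summaries for:

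- (a) weeks 0-24 on drug, all treated subjects, as the main safety table;
- (b) the extension, on drug;
- (c) off-drug follow-up.

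For each, give the number at risk, subject-weeks and events per 100 subject-weeks, and state the number extended. Define in advance to which period events soon after the last dose are assigned, given the half-life. Reconcile Section 4.1 with Section 6.4.2 on nonresponder follow-up, and Section 6.7.1 with Section 7.4.2 on the SAE window, so that the observation time in (c) is defined.

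The cost is wording and a few extra tables, with sparse counts in (b). AE onset and duration (Section 6.7) and self-administration dates in diaries (Section 5.6) are already collected, so splitting the summaries needs no new visits or procedures.

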|-----------------------------------|---|

|   |   |
|---|---|
| 
Criteria for Evaluation:
(Efficacy, safety,
stopping rules, etc.)
 | 
EFFICACY
 
Primary endpoint: SALT (Severity of Alopecia Tool) Scores: The proportion of scalp involvement is determined by dividing the scalp into 4 quadrants and estimating the percentage of the scalp surface that all the alopecic areas would occupy if placed together.
 
Secondary endpoint: Changes in hair re-growth as a continuous variable will be determined using physical exams and Canfield photography, as well as patient and physician global evaluation scores.
 
Differences in the incidence of regrowth between patients with patch type AA vs patients with alopecia totalis or universalis will also be analyzed on an exploratory basis.
 
In addition, response to abatacept treatment will be examined on an exploratory basis for correlation with the presence or absence of the AA GWAS risk haplotype.
 
Additionally, patient reported outcomes, safety measures, incidence and timing of relapse will be important secondary outcomes.
 
To assess safety, frequent and close monitoring of clinical and laboratory findings have been implemented. Adverse events will be captured and analyzed as a secondary endpoint.
 
All physical examination findings, vital sign abnormalities, and clinical laboratory abnormalities, will be captured as AEs when deemed medically significant by the investigator. A qualified physician associated with the study will be available to assess clinical signs and symptoms that may be indicative of an adverse event. Safety will be assessed by summarizing the incidence and type of AEs. The proportion of patients who discontinued treatment will be summarized.
 |
|---|---|

|                           |   |
|---------------------------|---|

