**Week 25 up to 72 (for subjects receiving optional additional treatment extension)**

Patient receiving an optional additional treatment extension of up to 6 months, at the discretion of the investigator, will continue to be seen every 6 weeks after week 24 while on the study medication, then at 12 weeks and 24 weeks after completion of up to 12 months of study drug, to determine durability or response or evidence for a delayed effects.

Efficacy evaluations: SALT, PGA, Patient global assessment and patient quality of life assessment will continued to be performed at every visit during optional additional treatment extension.

Blood draws for safety parameters will be conducted at 12 weeks after completion of study drug if deemed necessary to assess normalization of any previously abnormal values.

Adverse events will be assessed at every visit.

Standardized photographs of the subject's scalp will be done at every scheduled visit and will be used to support determination of percent hair regrowth. Photography will be performed using a high-resolution digital camera with Intellistudio system from Canfield Scientific, Inc. Patients will be positioned using a laser guide, after which photographs of the entire scalp will be taken at standardized locations and at a fixed distance. Close-up photographs may also be taken using an epiluminescent attachment in order to assess for the presence of early regrowth.

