#### Week 24 (Day 168 $\pm$ 7) – End of Treatment

- Vital signs, body weight
- Physical and dermatological examination
- Adverse events reporting, concomitant medication review
- Photography
- Physician evaluation utilizing the PGA and SALT scale
- Patient global assessment and quality of life assessment
- Urine pregnancy testing for WOCBP
- Clinical laboratory evaluation
- Scalp biopsy (4mm punch biopsy)
- Blood collection for immunological studies

Weeks 36 and 48 (Days 252 and 336  $\pm$ 7 days) – Observational Period

- Vital signs, body weight
- Physical and dermatological examination (only week 48)
- Adverse events reporting, concomitant medication review
- Photography
- Physician evaluation utilizing the PGA and SALT scale
- Patient global assessment and quality of life assessment
- Optional Scalp biopsy (4mm punch biopsy) – at the discretion of the principal investigator and with the consent of the subject, based upon perceived utility in context of individual patient response to therapy and durability of that response.
- Optional Blood collection for immunological studies, at the discretion of the principal investigator and with the consent of the subject.

Weeks 30, 36, 42, 48 (Extension Option)

Visit days will have an acceptable window of  $\pm$ 7 days.

- Vital signs, body weight
- Adverse events reporting, concomitant medication review
- Photography
- Physician evaluation utilizing the PGA and SALT scale
- Patient global assessment and quality of life assessment
- Urine pregnancy testing for WOCBP
- Physical and dermatological examination (week 36)
- Clinical laboratory evaluation, if indicated (at 12 weeks after end of study treatment)
- Optional Scalp biopsy (4mm punch biopsy) – at the discretion of the investigator and with the consent of the subject, based upon perceived utility in context of individual patient response to therapy and durability of that response.
- Optional Blood collection for immunological studies in addition to weeks 4 and 12, at the discretion of the investigator and with the consent of the subject.

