### **6.1.2 Study Drug Discontinuation**

If study drug administration is discontinued, the reason for discontinuation will be recorded.

Table 3: Schedule of Assessments

| Visit   | Screening | PPD reading | Base-line      | Week 4 | Week 8           | Week 12 | Week 18          | Week 24/ET | Week 30, 36, 42, 48 (optional) | 12 Weeks after end tx | 24 Weeks after end tx |
|---|-----------|-------------|----------------|--------|------------------|---------|------------------|------------|--------------------------------|-----------------------|-----------------------|
| Day   | -28 to -1 |             | 0              | 28±1   | 56±1             | 84±1    | 126±1            | 168±7      |                                |                       |                       |
| Informed Consent  | X         |             |                |        |                  |         |                  |            |                                |                       |                       |
| Inclusion/Exclusion Criteria  | X         |             | X              |        |                  |         |                  |            |                                |                       |                       |
| Medical History   | X         |             |                |        |                  |         |                  |            |                                |                       |                       |
| Body Weight   | X         |             | X              | X      | X                | X       | X                | X          | X                              | X                     | X                     |
| Physical/Cutaneous Exam   | X         |             |                |        |                  | X       |                  | X          |                                |                       | X                     |
| Vital Signs   | X         |             | X              | X      | X                | X       | X                | X          | X                              | X                     | X                     |
| Concomitant Medications   | X         |             | X              | X      | X                | X       | X                | X          | X                              | X                     | X                     |

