| Adverse events  |           |             | X              | X      | X                | X       | X                | X          | X                              | X                     | X                     |
| Photography   |           |             | X              | X      | X                | X       | X                | X          | X                              | X                     | X                     |
| SALT evaluation   | X         |             | X              | X      | X                | X       | X                | X          | X                              | X                     | X                     |
| Physician global assessment   | X         |             | X              | X      | X                | X       | X                | X          | X                              | X                     | X                     |
| Patient quality of life assessment  |           |             | X              |        |                  | X       |                  | X          | X                              | X                     | X                     |
| Patient global assessment   |           |             | X              |        |                  | X       |                  | X          | X                              | X                     | X                     |
| Clinical laboratory evaluation*   | X         |             |                | X      |                  | X       |                  | X          | X                              |                       |                       |
| Hepatitis screening panel, HIV test   | X         |             |                |        |                  |         |                  |            |                                |                       |                       |
| Lipid Profile   | X         |             |                |        |                  |         |                  |            |                                |                       |                       |
| PPD test and reading  | X         | X           |                |        |                  |         |                  |            |                                |                       |                       |
| Serum pregnancy test  | X         |             |                |        |                  |         |                  |            |                                |                       |                       |

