| Urine pregnancy test  |           |             | X              | X      | X                | X       | X                | X          | X                              |                       |                       |
| Scalp Biopsy  |           |             | X              | X      | (X) c | X       | (X) c | X          | (X) c               | (X) c      | (X) c      |
| Phlebotomy for immunological studies  |           |             | X d | X      | (X) c | X       | (X) c | X          | (X) c               | (X) c      | (X) c      |
| Training/reinforcement of training for self-administered SQ injection
Patient observed self-administering study medication |           |             | X b | X      | X                | X       | X                | X          | X                              |                       |                       |
| Chest X ray-1 view  | X         |             |                |        |                  |         |                  |            |                                |                       |                       |

aClinical laboratory evaluation consists of CBC, BMP, hepatic panel, and urinalysis. Additional evaluations will only be performed if needed to verify normalization of previously abnormal lab values.

bBaseline dose will be subcutaneous administration of abatacept.

c Optional additional Scalp biopsies (4mm punch biopsy) may be performed at the discretion of the investigator and with the consent of the subject, based upon perceived utility in context of individual patient response to therapy and durability of that response. Optional Blood collection for immunological may be performed at the discretion of the investigator and with the consent of the subject.

d Includes testing for AA GWAS risk haplotype

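### For extended subjects, Table 3 schedules laboratory tests at weeks 30, 36, 42 and 48, but Sections 6.1 and 4.1 give only a conditional draw after treatment ends

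*Combined protocol and SAP*

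**What the plan says.** The Synopsis allows 24 weeks of weekly dosing "with an option to extend treatment for up to an additional 24 weeks at the discretion of the investigator". It also describes the safety approach in strong terms: "To assess safety, frequent and close monitoring of clinical and laboratory findings have been implemented". Section 7.4.2 counts laboratory abnormalities among the safety outcomes ("Safety outcomes include adverse events, clinically significant changes in vital signs, laboratory test abnormalities, and clinical tolerability of the drug"), has clinically relevant ones entered as adverse events, and summarises adverse event incidence.

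Three places deal with laboratory tests in the extension:

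- **Table 3.** The row "Clinical laboratory evaluation" has an unbracketed X in the column headed "Week 30, 36, 42, 48 (optional" and nothing in the two columns for 12 and 24 weeks after treatment. A footnote to the table adds: "Additional evaluations will only be performed if needed to verify normalization of previously abnormal lab values".
- **Section 6.1, list for weeks 30, 36, 42 and 48 (Extension Option).** The entry reads "Clinical laboratory evaluation, if indicated (at 12 weeks after end of study treatment".
- **Section 4.1, extension subsection.** It says "Blood draws for safety parameters will be conducted at 12 weeks after completion of study drug if deemed necessary to assess normalization" of earlier abnormal values, and names no on-treatment draw.

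**The concern.** The planned analysis of laboratory safety runs through adverse events: a test is done, an abnormal result is judged relevant, it becomes an adverse event, and its incidence is summarised. What the summary can contain therefore depends on which tests are done. For extended subjects the visit list that a site would work from and the schedule table give different answers.

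If the Section 6.1 entry is followed as written, subjects receive up to 24 further weekly doses with no scheduled blood count, chemistry, hepatic panel or urinalysis. A silent fall in counts or rise in transaminases beginning after week 24 would not be looked for on schedule. It could then reach the Section 7.4.2 summary late or not at all, and could fail to prompt the interruption that Section 5.3.1 ties to laboratory evidence of toxicity. The subjects concerned have up to twice the planned exposure.

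**Working it through.** The plan gives no figure for laboratory testing that could be reproduced. Its one design figure, 80.7% power, is not an input here. (For 15 subjects and 40% against 10%, a two-sided arcsine calculation gives 80.3%, close to the stated value.) The check is a comparison of the three sources and a count.

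**Sources side by side**

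| Source | Weeks 4, 12, 24 | Weeks 30, 36, 42, 48 on extended treatment | 12 weeks after treatment ends |
|---|---|---|---|
| Table 3 | marked | marked, unbracketed | no mark |
| Section 6.1 | listed | conditional, and timed after treatment | not in the observational-period list; appears only in the extension list |
| Section 4.1 | deferred to the table of procedures | not mentioned | conditional, to check normalization |

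**Is the Table 3 mark reliable?** The row's other marks (screening, weeks 4, 12 and 24) agree with the Section 6.1 lists, so a shifted column is unlikely. In the same extension column, biopsy and immunology blood carry a bracketed X, footnoted as optional. The table therefore separates optional from scheduled items, and the laboratory mark reads as scheduled. The footnote on additional evaluations most naturally covers tests beyond those marked. If it were read as making the extension mark conditional too, the sources would conflict less, but no laboratory test would be scheduled in the extension at all.

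**Scheduled on-treatment sets after baseline, subject treated to week 48**

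- Table 3: 3 (weeks 4, 12, 24) + 4 (weeks 30, 36, 42, 48) = 7.
- Section 6.1 as written: 3 + 0 = 3.
- Difference: 7 − 3 = 4, all in the extension.

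**Longest on-treatment interval between scheduled tests**

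- First 24 weeks: 24 − 12 = 12 weeks.
- Extension under Table 3: 30 − 24 = 6 weeks.
- Extension under Section 6.1: 48 − 24 = 24 weeks, with no test scheduled at its end.

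The draw named in Sections 6.1 and 4.1 would fall at 48 + 12 = week 60. That is 60 − 24 = 36 weeks after the week 24 sample, and the draw is conditional. Week 60 is also not one of the visits in the list where Section 6.1 places the item.

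**The case against.** The best defence is that Table 3 governs. Section 4.1 says that scheduled visits are outlined in the table of assessments. Section 6.1 opens by saying that Table 3 summarizes frequency and timing. Section 4.1 also sends safety blood draws to the table. On this view the Section 6.1 entry is a drafting slip, since a post-treatment timing does not belong in an on-treatment visit list, and no gap exists. This is probably the intent. But neither an outline nor a summary is stated to override the visit lists, and the deferral of blood draws to the table sits in the subsection for baseline to week 24. The extension subsection gives its own timing, and a slip in an operative visit list can still be followed.

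Two parts of the defence stand in full:

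- Section 4.1 is silent on on-treatment draws in the extension. A reader might infer that it rules them out, but it does not say that the post-treatment draw is the only one.
- A reader might infer that week 60 is the next possible test under Section 6.1. It is not. Section 6.1 allows an evaluation when indicated, lists one at early termination, and permits unscheduled visits at any time. Section 4.1 likewise requires evaluations when treatment stops early. The zero counts scheduled tests only.

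**Conclusion.** The inconsistency is real and is in the current text. Its firm size is 4 scheduled on-treatment laboratory sets against 0 for each subject treated to week 48, and a longest scheduled gap of 6 weeks against 24. The consequence is possible late or missed detection of symptom-free abnormalities that begin after week 24, and it assumes that a site follows Section 6.1 as written.

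A reader might want a count or probability of missed events. The documents do not support one: they give neither the number of subjects to be extended nor a rate of such abnormalities. Section 1.3.4 reports one of 40 healthy subjects with laboratory changes recorded as adverse events after a single subcutaneous dose. That shows the kind of event can occur, but it is not a rate for weekly dosing in alopecia areata.

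A reader might also infer that the Section 7.4.2 analysis is itself defective. It is not: incidence of adverse events in all dosed subjects, with relevant laboratory findings recorded as such, is a stated and adequate descriptive analysis for a pilot. Shift tables and separate denominators would be optional reporting detail.

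Subjects who are not extended, the week 24 primary endpoint, the sample size of 15 and the power are unaffected. The correction should be made, but it does not bear on the efficacy conclusion.

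**What to change.** 1. In the Section 6.1 extension list, replace the laboratory entry with: *Clinical laboratory evaluation (CBC, BMP, hepatic panel, urinalysis) at weeks 30, 36, 42 and 48 while on extended treatment.*
2. State the same schedule in the Section 4.1 extension subsection.
3. Move the conditional draw at 12 weeks after treatment to the Section 6.1 list for the observational period after extension, and mark it as conditional in the matching Table 3 column.

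The cost is a few lines of wording. Relative to Table 3 there are no new tests. Relative to the Section 6.1 text there are up to 4 blood and urine sets per extended subject, or 4 × 15 = 60 if all 15 were extended to week 48. These fall at visits already planned every 6 weeks, and Section 6.2 says laboratory testing is supplied free of charge. Section 7.4.2 needs no change.
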